**NCT Number 02473471**

**February 21, 2017**

## **MATERIAL AND METHODS:**

### **Trial design and any changes after trial**

#### **Commencement**

This study was a split mouth randomized clinical trial with a 1:1 allocation. Methods were not changed after trial initiation.

### **Participants, eligibility criteria, and settings**

Ethical approval was obtained from Institutional Review Board (IRB) at King Abdullah University Hospital /Jordanian University of Science and Technology (JUST) with approval No.: 20150263. This trial was also registered at ClinicalTrials.gov with identifier number: NCT02473471. Participants were recruited from new patients attending the orthodontic department at the Postgraduate Dental Clinics at JUST. The following inclusion criteria were applied: (1) Males and females, (2)  $\geq 16$  Years old, (3) Class II division 1 malocclusion, (4) Class II canine relationship, (5) Average lower facial height (LFH) and maxillary mandibular plane angle (MMPA); patients with LFH ranging from 53 to 57 percent ( $55 \pm 2$ ) and with MMPA ranging from 23 to 31 degrees ( $27 \pm 4$ ) were only considered based on Eastman cephalometric standards. The exclusion criteria were: (1) diseases/ medications that are likely to affect bone biology, (2) poor oral hygiene, (3) low and high angle cases, (4) previous orthodontic treatment, (5) Evidence of bone loss, (6) active periodontal disease, (7) Smokers. Patients were selected according to the inclusion/ exclusion criteria during the recruitment time. Subsequently, the patients were invited to sign a consent form after clarifying the purpose of the intervention and the associated risks and benefits.

### **Sample size calculation**

The sample size was calculated based on a type I error frequency of 5%. According to the power analysis and assuming a large effect size difference between groups (effect size= 0.8), the power analysis yielded 28 subjects per group at a conventional alpha level ( $p = 0.05$ ) and desired power ( $1 - \beta$ ) of 0.90, yielding a total sample size estimate of 56 subjects. All calculations were performed with the computer application G-Power .

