## **Randomization (random number generation, allocation concealment, implementation)**

The intervention was randomly allocated to either right or left side with 1:1 allocation ratio. The randomization was accomplished using the permuted random block size of 2 with random generation function in Excel (Microsoft, Washington). Subsequently, the random sequence to either right or left were concealed in opaque envelopes and shuffled before the intervention to increase the unpredictability of the random allocation sequence. Each patient was asked to pick one sealed envelope to assign to the surgical intervention either on the right or the left side. Allocation concealment was aimed to prevent selection bias and protect the assignment sequence until allocation.

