### **Clinical Micro-osteoperforations Procedure**

MOPs were performed when the canines were ready to be retracted. The patients were asked to rinse their mouth twice by chlorhexidine for 1 minute. Local anesthesia was then given (2% lidocaine with 1:100,000 epinephrine, Septodont, France). MOPs were also performed by one investigator as judged by the randomization process either on the right or left upper canines as the following:

- a) MOP with 1.5 mm width and 3 to 4 mm depth inside the bone was applied. MOPs were performed using miniscrews (Aarhus Mini-implant system, American Orthodontics) of 1.5 mm diameter and 6 mm length in 3 points distal to canine.
- b) The points of screws insertion were demarcated by bleeding points using the calibrated periodontal probe. One row consisting of 3 holes was made distal to the canine.
- c) For standardization of the protocol, the exact location of screw insertion was determined as the following: the first dot was located 3mm distal to canine and 6 mm from the free gingival margin. The second point was marked 5 mm from the first one. The net distances between MOP after insertion of 1.5 mm diameter miniscrews were 3 mm between each

hole and 2 mm away from the contact point and 5 mm away from the free gingival margin (Figure 1).

- d) The miniscrew length of 6 mm was used to be inserted 3 to 4 mm deep into the bone and to account for the thickness of the soft tissue of about 2 to 3 mm.

After application of MOP, the extraction space was started to be closed using NiTi close coil spring connecting from the miniscrews between upper second premolar and first molar to power arm extended from the vertical slot of the upper canine bracket (3M Unitek, 9mm, 150g) (see Figure 3). The force was measured by force gauge (Correx, Dentaurum, Germany) at the day of application to ensure the constant and equal amount of force between all subjects and also between experimental and control sides.

After the intervention, the patients were instructed to take analgesics, such acetaminophen/Tylenol, only if necessary. Anti-inflammatory NSAIDs were avoided because of their known effect on tooth movement. Maintaining good oral hygiene and using chlorhexidine 0.2%, twice a day for five days, were recommended.

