#### **Statistical analysis (primary and secondary outcomes, subgroup analyses)**

Statistical analysis was accomplished using the Statistical Package for the Social Sciences computer software (SPSS 20.0, SPSS Inc., IL, USA). Probability values equal or less than 0.05 were considered significant. Independent sample t-tests were calculated to analyze the results of the primary outcome and secondary outcomes to compare the difference between MOP and control sides. Similarly, independent sample t-test was performed to compare the amount of root resorption before and after three months in MOP and control sides separately. Chi-square was used for analysis of categorical data including the willingness to repeat the procedure and recommend it to a friend. Descriptive statistics were used to describe the satisfaction and ease of the procedure.

Reliability coefficient (Cronbach's Alpha) was used to evaluate the reliability of measurements of primary outcomes. One examiner did all measurements, and all subjects were randomly selected. Six of 3D superimposed digital models had been chosen randomly. Superimpositions on the rugae area and canine displacement were measured twice within 2-week interval. Reliability coefficient (Cronbach's Alpha) was 0.95, showing excellent superimpositions and measurement agreement.

For intraoral measurements, intra-examiner reliability was done in the lower arch after reaching 0.019x0.025 stainless steel arch wire and teeth were in a passive state; all cases were non-extraction in the lower arch. Six of subjects were selected randomly, and measurements were done twice with the 2-week interval. Measurements were done from the upper mesial wings of the lower canine bracket to the upper distal wing of the lower second premolar bracket. Reliability coefficient (Cronbach's Alpha) was 1.00, indicating excellent measurement agreement.

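### The trial is split-mouth, but it is sized in separate groups of subjects and analysed with unpaired tests, so the planned patient number and the basis of the 90% power are unclear

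*Combined protocol and SAP*

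**What the plan says.** The trial design section states: "This study was a split mouth randomized clinical trial with a 1:1 allocation". The randomization section makes the side of the mouth the unit allocated: "Each patient was asked to pick one sealed envelope to assign to the surgical intervention either on the right or the left side". The section on the MOP procedure likewise contrasts sides within patients, asking for an "equal amount of force between all subjects and also between experimental and control sides".

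The sample size section uses other terms. It starts from "assuming a large effect size difference between groups (effect size= 0.8", a 5% type I error and 90% power, and reports that "the power analysis yielded 28 subjects per group at a conventional alpha level", "yielding a total sample size estimate of 56 subjects". It names G-Power as the software. It gives no test, number of tails, raw difference, SD or within-patient correlation.

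The statistical analysis section says: "Independent sample t-tests were calculated to analyze the results of the primary outcome". It uses the same test for the secondary comparisons between the sides, and for root measurements before and after three months within each side. It sets a 0.05 threshold without saying one-sided or two-sided.

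The design section also states: "Methods were not changed after trial initiation".

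**The concern.** In a split-mouth trial there are no two groups of subjects, because one patient contributes to both arms. Two problems follow.

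First, the planned number of patients cannot be read from the text. Twenty-eight patients already provide 56 sides, so a total of 56 could count sides or patients. No other section gives a patient count.

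Second, the two sides of one mouth share a patient, and their results may be correlated. An independent-samples t-test takes that correlation as zero. If it is positive, the test overstates the standard error of the difference, and the stated 5% error rate and the power no longer describe the test that is run.

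A lesser concern is the 90% itself. A reader would probably take it as the power of a two-sided comparison suited to this design, and the section does not support that reading.

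**Working it through.** **Inputs.** Effect size 0.8, alpha 0.05, power 0.90, 28 per group and 56 in total come from the sample size section. The within-patient correlation ρ is not in the documents; every value of it below is an assumption. Power is exact, from the noncentral t distribution.

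**Step 1: reproduce the stated 28.** For two independent groups of n, the noncentrality is 0.8 × √(n/2) on 2n − 2 degrees of freedom. At n = 28 it is 0.8 × √14 = 2.99.

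| Independent t-test | n per group | Power |
|---|---|---|
| one-sided | 27 | 89.5% |
| one-sided | 28 | 90.5% |
| two-sided | 28 | 83.6% |
| two-sided | 33 | 89.3% |
| two-sided | 34 | 90.2% |

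The stated 28 is therefore exactly the one-sided answer. The two-sided answer is 34.

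**Step 2: try paired calculations.** For n pairs the noncentrality is dz × √n on n − 1 degrees of freedom.

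- If 0.8 is the standardized within-patient difference (dz = 0.8), the required number is 15 pairs one-sided or 19 two-sided. Twenty-eight pairs give 98.3% two-sided, so 28 more than suffices but is not the required number.
- If 0.8 is on the SD of one side, dz = 0.8/√(2(1 − ρ)). Two-sided, exactly 28 pairs are required when ρ is about 0.21 (28 pairs reach 90%) to 0.24 (27 would do). One-sided, the range is about 0.01 to 0.04.

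**Step 3: two-sided paired power, with 0.8 on the SD of one side.**

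| Assumed ρ | dz | 28 patients | 56 patients |
|---|---|---|---|
| −0.2 | 0.516 | 75.0% | 96.7% |
| 0 | 0.566 | 82.3% | 98.6% |
| 0.2 | 0.632 | 89.7% | above 98.6% |
| 0.3 | 0.676 | 93.2% | above 98.6% |
| 0.5 | 0.800 | 98.3% | above 98.6% |

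**Step 4: the planned test on paired data.** With a common SD σ, the difference in side means has variance 2σ²(1 − ρ)/n, while the independent t-test estimates 2σ²/n. Simulating the two-sided independent t-test on 28 bivariate normal pairs (400,000 runs per ρ, shift of 0.8 SD for power) gives:

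| Assumed ρ | True type I error (nominal 5%) | Power, independent test | Power, paired test |
|---|---|---|---|
| 0 | 5.0% | 83.6% | 82.3% |
| 0.2 | 2.9% | 86.2% | 89.7% |
| 0.3 | 2.0% | 87.7% | 93.2% |
| 0.5 | 0.7% | 91.2% | 98.3% |

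With positive correlation the planned test is conservative and gives up power. With zero correlation the paired test is about 1.4 points worse. By the variance formula, a negative correlation would make the unpaired test anti-conservative.

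**The case against.** Several points on the other side have force.

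- **The 28 is not miscalculated.** It reproduces exactly under one standard calculation. The fault is a mismatch between design and analysis plus an undeclared assumption, not an arithmetic slip. This stands.
- **The basis of the 28 is inferred.** The sample size section names no test; only the analysis section does. A reader might infer that the trial was planned one-sided, or that 28 reaches 90% only that way. Neither is supported. A paired two-sided calculation with ρ of about 0.21 to 0.24 also requires 28, and 28 pairs with 0.8 as the within-patient effect exceed 90% comfortably. What holds is narrower: with no correlation added, 28 is the *required* number only for the one-sided independent test.
- **Subjects elsewhere means patients.** The interventions section and the MOP procedure section use the word that way, and the latter sets subjects apart from sides. This favours 56 patients, with ample paired power. It does not settle the count, because 28 per group then has no explanation.
- **The 83.6% describes a trial that was not run.** That is fair: there are no independent groups here, so by itself the sidedness gap is a minor reporting matter. The weight rests on the patient number and the unpaired tests.
- **Restating power for completed work changes nothing in the design.** This is true, and a power recalculated from the results would be of no use. Planning power at the planned number is different: it replaces a quoted figure that has no clear meaning.

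**Conclusion.** The point holds as a mismatch of design and analysis and should be corrected. Two parts need no assumption: the planned number of patients is not identifiable, and the tests for within-patient comparisons ignore the pairing. The size of the second depends on an unstated ρ. For 28 pairs with positive correlation up to 0.5, true type I error falls to between 2.9% (ρ = 0.2) and 0.7% (ρ = 0.5), and at ρ = 0.5 about 7 points of power are lost (91% against 98%).

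The sidedness point is secondary and inferred. The 90% cannot be quoted without saying which test, which tails and which SD it refers to.

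A reader might conclude that the trial was underpowered. The documents do not show this. With 0.8 on the SD of one side, 28 patients reach 90% two-sided with a paired test once ρ is about 0.21. With 56 patients, power is at least 98.6% for any ρ of zero or more.

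**What to change.** **Statistical analysis section.** Replace the independent-samples t-test with a two-sided paired t-test for the primary MOP-versus-control comparison, for the secondary comparisons between sides, and for before-versus-after root length in the same teeth. Disclose this as a later correction, and reconcile it with the design section's statement that "Methods were not changed after trial initiation".

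**Sample size section.**

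1. State the number of patients and the number of sides.
2. State the test and sidedness from the G-Power record, or say that they are not documented. If the calculation was one-sided on independent groups, add that the two-sided power on that basis is 83.6%.
3. Say which SD the 0.8 refers to.
4. Replace the bare 90% with the planning power of a two-sided paired t-test at the planned number of patients, with ρ labelled as an assumption. For 28 patients this is 75%, 82%, 89.7%, 93% and 98% at ρ of −0.2, 0, 0.2, 0.3 and 0.5 if 0.8 is on the SD of one side, or 98% if it is the within-patient standardized difference. For 56 patients, on the SD of one side, it is at least 98.6% for ρ ≥ 0 and 96.7% at ρ = −0.2.

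**Cost.** One check of the software record, a few reworded sentences and a rerun of the comparisons on the same data; no extra patients. The downsides are a possibly less favourable quoted power, about 1.4 points of power lost at 28 patients if the sides are uncorrelated, and a late change of test that must be disclosed.

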## **Randomization (random number generation, allocation concealment, implementation)**

The intervention was randomly allocated to either right or left side with 1:1 allocation ratio. The randomization was accomplished using the permuted random block size of 2 with random generation function in Excel (Microsoft, Washington). Subsequently, the random sequence to either right or left were concealed in opaque envelopes and shuffled before the intervention to increase the unpredictability of the random allocation sequence. Each patient was asked to pick one sealed envelope to assign to the surgical intervention either on the right or the left side. Allocation concealment was aimed to prevent selection bias and protect the assignment sequence until allocation.

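### Right or left side is what the trial randomises, but the planned independent t-tests use neither the within-patient pairing nor the side: pairing is the larger loss, and a side term is a near-free refinement.

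*Combined protocol and SAP*

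**What the plan says.** The trial design paragraph says: "This study was a split mouth randomized clinical trial with a 1:1 allocation". In the section on randomization, the unit of allocation is the side of the mouth: "The intervention was randomly allocated to either right or left side with 1:1 allocation ratio". Two details there bear on balance. The list was restricted: "The randomization was accomplished using the permuted random block size of 2". After that, the assignments "were concealed in opaque envelopes and shuffled before the intervention", and the order of use was left to chance: "Each patient was asked to pick one sealed envelope".

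The section on statistical analysis applies independent-sample t-tests to the primary and secondary outcomes "to compare the difference between MOP and control sides". The only decision rule is: "Probability values equal or less than 0.05 were considered significant". The document contains no paired test, no term for right or left, no analysis by side, and no report of how many patients had MOP on each side.

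**The concern.** In a split-mouth trial, right/left plays the part that period plays in a crossover. Each patient supplies both levels, and randomisation decides which level gets the treatment. Blocks of 2 show an intention to balance it. An analysis that follows the design would work on within-patient differences and allow for side.

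The plan does neither, which has two consequences.

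- **Pairing.** If the two sides of one mouth respond alike, the independent t-test uses a standard error that is too large. It is then conservative and gives up power.
- **Side.** One resident treats every patient, one investigator performs all MOPs and one examiner makes all measurements. A right-left habit, if there is one, would therefore recur across patients. Under a balanced split it would be counted as random error. Under an unequal split, part of it would be added to the MOP estimate from that allocation. Pairing alone does not remove it.

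**Working it through.** **Inputs from the documents:** effect size 0.8, alpha 0.05, power 0.90, 28 per group and 56 in total (sample size section); 1:1 allocation of side in blocks of 2 (randomization section); independent t-tests (statistical analysis section).

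**Assumptions, not in the documents:** 28 patients with two sides each (the 56 subjects could also be read as 56 patients); outcome SD 1; within-patient correlation ρ of 0 or 0.5; right-minus-left difference g from 0 to 0.5 SD; two-sided 0.05 tests.

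**1. The plan's own figure.** For two independent groups, n per group = 2(z₁₋α + z₀.₉₀)²/0.8².

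- One-sided: 2(1.645 + 1.282)²/0.64 = 26.8. The exact t version gives 27.5, rounded up to 28, with power 0.905 at 28.
- Two-sided: 2(1.960 + 1.282)²/0.64 = 32.8. The exact t version gives 34, and power at 28 is 0.836.

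So 28 reproduces as a one-sided calculation for independent groups. Neither pairing nor side enters it.

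**2. Balanced split: g goes into the error.** Write a patient's difference as D = δ + g·z + e, with z = +1 if MOP is on the right and −1 if on the left, and Var(e) = 2(1 − ρ).

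- Paired test without side: variance is multiplied by 1 + g²/(2(1 − ρ)). At ρ = 0.5 this is 1.04 for g = 0.2 and 1.25 for g = 0.5.
- Planned independent test: the variance it uses is multiplied by 1 + g²/4, which is 1.01 and 1.06.

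Simulated power (20,000 trials per setting, 14/14, effect 0.8):

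| ρ | g | Independent (planned) | Paired | Paired with side |
|---|---|---|---|---|
| 0.5 | 0 | 0.914 | 0.984 | 0.984 |
| 0.5 | 0.2 | 0.910 | 0.981 | 0.983 |
| 0.5 | 0.5 | 0.897 | 0.969 | 0.983 |
| 0 | 0 | 0.833 | 0.820 | 0.819 |
| 0 | 0.5 | 0.823 | 0.789 | 0.823 |

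At ρ = 0.5, a side effect of 0.5 SD costs the planned test 0.914 − 0.897 = 1.7 points and a paired test 0.984 − 0.969 = 1.5 points. Other simulation runs put both at about 1 point. Ignoring the pairing costs 0.984 − 0.914 = 7 points at g = 0. With no treatment effect, ρ = 0.5 and g = 0, the independent test rejects in 0.006 to 0.007 of trials, not 0.05. If ρ is 0, pairing gains nothing and loses about 1 point.

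**3. Unequal split: a shift conditional on that split.** Without a side term the estimate moves by g(nR − nL)/n.

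| Split | (nR − nL)/n | g = 0.2 | g = 0.5 |
|---|---|---|---|
| 16/12 | 4/28 = 0.143 | 0.029 | 0.071 |
| 18/10 | 8/28 = 0.286 | 0.057 | 0.143 |
| 20/8 | 12/28 = 0.429 | 0.086 | 0.214 |

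With side in the model the estimate returns to 0.80 within simulation error. At 20/8, g = 0.5, ρ = 0.5 and no treatment effect, the rejection rate is 0.144 for the paired test without side, 0.048 with side, and 0.045 for the planned test.

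**4. How likely is imbalance?** Blocks of 2 give equal numbers in the set of envelopes prepared. If all are used, the allocated split is equal whatever the shuffling. If only some are used, it need not be. As an illustration, 28 envelopes drawn from 56 give 17/11 or worse with probability 0.18, and 18/10 or worse with probability 0.06. The number prepared is not stated.

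**5. Cost of the side term.** With 28 patients the critical t goes from 2.052 (27 df) to 2.056 (26 df). If the split is unequal, the variance of the intercept is also multiplied by 1/(1 − ((nR − nL)/n)²). At 18/10 that is 1/(1 − 0.0816) = 1.09, and simulated power goes from 0.984 to 0.974 at ρ = 0.5 and g = 0.

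**The case against.** The strongest reply is that a side effect is nowhere shown. The spring force was measured so as to be equal on the two sides, occlusal interferences were checked weekly, and the digital models were coded and measured against a standard reference plane. Canine displacement and root resorption are changes from the same tooth's baseline, so a constant right-left measuring offset cancels. Under the specified balance, the error from omitting side is conservative and creates no false-positive risk. Most of the gain from the proposed analysis comes from pairing. All of this stands, and it is why the side term ranks as a refinement.

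Two stronger readings are tempting, and the documents support neither.

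- **A large power loss.** A paired test set up to have 90% power at an effect of 0.636 SD falls to 89%, 85% and 78% for side effects of 0.25, 0.5 and 0.75 SD of the difference. But the plan contains no paired test and assumes 0.8, and the last case needs a side effect larger than the treatment effect.
- **A biased MOP effect.** The shift in step 3 needs an unequal split, for which the documents give no evidence, and it is conditional on that split. Over repeated randomisation the unadjusted estimate is unbiased.

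The reply does not dispose of the mismatch itself. The analysis ignores both the pairing and the factor that was randomised. Correcting the pairing alone makes any side effect a larger share of the remaining error (1.25-fold against 1.06-fold at g = 0.5, ρ = 0.5).

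**Conclusion.** The point holds in a limited form. The planned tests do not follow the split-mouth randomisation, because they use neither the pairing nor the side. At 28 patients, ρ = 0.5, a 14/14 split and effect 0.8, leaving out side costs 1 to 2 points of power for side effects up to 0.5 SD; at ρ = 0 it costs a paired test about 3 points. Ignoring the pairing is the larger loss at ρ = 0.5: power of about 0.91 against 0.98, with an actual type I error of about 0.007 in place of 0.05. The size of g, the value of ρ and the achieved split are all unknown from the documents. A reader should not conclude that the MOP estimate is biased by design or that a right-left effect is present. The documents show only that the analysis could neither detect nor remove one.

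**What to change.** For each outcome compared between sides, compute the patient's MOP-minus-control difference. Regress it on an indicator of the side that received MOP (+1 right, −1 left). Take the intercept with its 95% CI as the MOP effect. Report the side coefficient, the number of patients with MOP on each side, and the number of envelopes prepared.

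This takes one or two sentences in the statistical analysis section and uses only the allocation list and data already collected. Under a balanced split the cost of the side term is one degree of freedom (critical t 2.052 to 2.056); under an unequal split there is also the modest variance increase shown above. Working on within-patient differences is the part that matters most. The side term is a near-free addition to it and optional in priority.

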## **Blinding**

Blinding of either patient or clinician was not possible. The blinding was ensured at measurement stage (data collection), in which the investigator was blinded of where MOPs were applied to either right or left by coding all digital models.

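### Permuted blocks of 2 are stated, but shuffling the envelopes and letting patients pick makes the allocation a random draw without replacement, balanced right/left for certain only if every envelope is used

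*Combined protocol and SAP*

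**What the plan says.** The trial design section states: "This study was a split mouth randomized clinical trial with a 1:1 allocation". What is randomised is therefore the side within the patient, and the Randomization section confirms this: "The intervention was randomly allocated to either right or left side with 1:1 allocation ratio".

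The same section describes three steps:

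- Generation: "The randomization was accomplished using the permuted random block size of 2 with random generation function in Excel".
- Preparation: the sequence was "concealed in opaque envelopes and shuffled before the intervention to increase the unpredictability of the random allocation sequence".
- Assignment: "Each patient was asked to pick one sealed envelope to assign to the surgical intervention either on the right or the left side".

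It does not give the number of envelopes, whether all of them or only a subset were shuffled together, whether they were numbered, whether draws were logged, or what happened to an opened envelope if MOP was not then done. The Blinding section adds: "Blinding of either patient or clinician was not possible". The Statistical analysis section plans independent-sample t-tests of MOP against control sides and has no term for right or left.

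**The concern.** A permuted-block list has its balancing property only when it is applied in the order generated. Shuffling the envelopes and letting the patient choose replaces that order with another random order. The plan then claims a property, blocking in pairs, that the procedure does not have.

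The stake is right/left balance. If canines on one side move faster for reasons unrelated to MOP, that difference enters the MOP-minus-control estimate in proportion to the excess of one side among the MOP sides. The planned analysis has nothing to remove it. A second, smaller matter is that the text describes no way of matching opened envelopes to patients.

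**Working it through.** **Step 1. Which procedure was used?** There are two readings.

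- The shuffle was confined to each pair. The blocks survive, but the shuffle adds nothing, because the order within a pair was already random. The second allocation of each pair is still known once the first is seen.
- The envelopes were shuffled together. This fits the stated purpose of making the sequence less predictable, and it is the natural reading. The block order is then gone, and each patient draws without replacement from a pool that is half right and half left.

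**Step 2. Number of envelopes.** The Sample size calculation section gives 28 per group and 56 in total, for effect size 0.8, alpha 0.05 and power 0.90. The figure of 28 reproduces as a one-sided two-group t-test (power 0.905); the two-sided version needs 34 per group. Nothing below depends on that calculation. The 28 serves only as an assumed pool size: 28 patients with two sides each, and one envelope per patient. A pool of 56 is shown for range.

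**Step 3. Right/left gap.** Blocks of 2 applied in order keep the gap at 1 or less throughout. In a shuffled pool with equal halves, the gap among used envelopes equals the gap among unused ones, so it is enough to count the unused envelopes.

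- All 28 used: gap 0.
- 26 of 28 used (2 left over, C(28,2) = 378 possible pairs): P(gap 0) = 14 × 14 / 378 = 0.52; P(gap 2) = 2 × C(14,2) / 378 = 182/378 = 0.48. The maximum is 2.
- 24 of 28 used (4 left over, C(28,4) = 20,475 possible sets): P(gap 0) = 91² / 20,475 = 0.40; P(gap 2) = 2 × 364 × 14 / 20,475 = 0.50; P(gap 4) = 2 × 1,001 / 20,475 = 0.098. The maximum is 4, and the mean gap is 1.4.
- 52 of 56 used: the maximum is again 4, with probability 2 × 20,475 / 367,290 = 0.11.

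**Step 4. Effect on the estimate.** Let t be the MOP effect, d a natural right-minus-left difference, and R and L the numbers of patients with MOP on the right and on the left. A patient with MOP on the right contributes t + d on average, and one with MOP on the left contributes t − d. The mean over N = R + L patients is

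t + d × (R − L)/N.

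The share of d carried over is at most 2/26 = 8% with 26 of 28 used, 4/24 = 17% with 24 of 28 used, and 4/52 = 8% with 52 of 56 used. If d is zero, nothing is carried over.

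**Step 5. What the shuffle gains.** With fixed blocks of 2 in order, an observer guesses right half the time on the first of each pair and always on the second, so 75% overall. For a shuffled pool, always naming the side drawn less often so far is right about 60% of the time (28 envelopes) or 58% (56 envelopes).

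**The case against.** The strongest reply is that this is a fault of description, not of conduct. A draw without replacement is a valid randomisation with tighter balance than coin tossing. Chance imbalance adds variance but does not bias the estimate over repeated allocations. Each patient supplies one MOP side and one control side, so the arms stay equal and patient characteristics stay matched whatever the right/left split. The shuffle answers a real weakness of fixed blocks of 2 in a trial without blinding of patient or clinician. The documents show no right/left difference in canine movement; the force is measured so as to be equal on both sides, and the digital models are coded before measurement. On either reading of the sample size, the planned enrolment uses the whole set, and the gap is then zero.

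All of that stands, and it limits the size of the point. It does not make the stated block size true, and it does not cover a set left partly unused.

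A reader might also pair 28 patients with 56 envelopes and obtain a gap of 4 or more with probability 0.42, a gap of 6 or more with probability 0.18, and a carry-over of 6/28 = 21%. The arithmetic is right, but that pairing takes both readings of the sample size at once and needs a half-used pool, which no section suggests.

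**Conclusion.** The point holds as a misdescription with a bounded consequence. Unless the shuffle was confined to each pair, the allocation was a random draw without replacement, and right/left balance is guaranteed only when every envelope is used. Assuming 28 envelopes, and taking 24 used as the less favourable case, the gap is at most 4, reached with probability 0.10, and at most 17% of any right/left difference enters the MOP estimate. The pool size, the number unused and the existence of a right/left difference are all assumptions, because the documents give none of them.

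Three stronger inferences are not supported. Balance is not lost whenever envelopes remain: exact balance still has probability 0.52 at 26 of 28 and 0.40 at 24 of 28. It also cannot be said that draws were untraceable or that an inconvenient side was redrawn. The text describes no numbering or log, but it does not exclude them, and it has the patient picking a sealed envelope. Finally, neither the randomness of the allocation nor the equality of the arms is in doubt.

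**What to change.** The document is written in the past tense and reports completed reliability checks, so the envelopes have probably been drawn. In that case:

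- Replace the statement of permuted blocks of 2 with random draw without replacement or, if the shuffle was within pairs, say so.
- Report the number of envelopes prepared and the right/left counts obtained, including any envelope opened for a patient who was not then treated. State whether envelopes were numbered and draws logged.
- Include side (right/left) as a term in the within-patient comparison. This requires analysing each patient's MOP-minus-control difference, not the two sides as independent samples.

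The cost is a text correction and one model term. At a 14:10 split, the variance multiplier of the side-adjusted estimate is (1/4)(1/14 + 1/10) = 0.0429 against 1/24 = 0.0417, a rise of about 3%.

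If allocation is still to be done, generate the list with undisclosed mixed block sizes and number the sealed opaque envelopes in that order. Open them strictly in sequence, with patient identifier and date recorded, and delete the shuffle and the patient's pick. This needs a log but no extra patients or visits. The downside is that mixed blocks of, say, 4 and 6 allow a gap of up to 3 in an unfinished block, more than blocks of 2 would. Simply restoring blocks of 2 in order is not advised, because every second allocation would then be predictable.
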